## 2. METHOD

### 2.1. Study Design

Based in a university clinic, youth will be randomly assigned, stratified by sex and age (10-14, 15-18), in a 1:1 parallel group design, to receive either TranS-C or PE. Sibling pairs will be randomized to the same condition.

Assessors will be blind to treatment allocation. Sequentially numbered, opaque, sealed envelopes will be generated using a computer-generated random number list. A project coordinator will conduct randomization after all eligibility assessments are completed. Assessments will be conducted at baseline and at the end of treatment. The Committee for the Protection of Human Subjects approved the study.

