## 5. DATA ANALYSIS

Sample size will be determined via power analysis. Power analyses will be conducted based on the average of Cohen's  $d$  (0.48) across estimations of the effect of treatment on sleep duration (for sleep outcomes) and the five primary health outcomes. Specifically, for sleep outcomes Cohen's  $d$  will be calculated from the pre-post deviation scores across TranS-C and Psychoeducation conditions. For the five health domains we will use: our pilot data for emotional health and behavioral health recent meta-analyses for cognitive health and physical health; and unpublished data from a collaborator's lab for the impact of poor sleep on social interactions. G\*Power 3.1 was used to estimate sample size using Cohen's  $d = 0.48$ , assuming significance of 0.05 and power of at least 80%. Sixty nine participants are needed for each condition. We will recruit 20% more for potential attrition. There will be no interim analyses.

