Data analysis will be conducted in Stata 14 (StataCorp, 2015). All analyses will be adjusted for age and sex, which will be the stratification factors used during randomization. Using intent-to-treat, multilevel modeling with maximum likelihood estimation with the assumption of missing at random will be used to examine continuous outcomes. The fixed component of the model will include stratification factors (age and sex), an indicator for time period (Time=0 pre-treatment, Time=1 post-treatment), an indicator for treatment condition (Treatment=1 TranS-C, Treatment=0 PE), and a Time by Treatment interaction term. The random part of the model will include a subject-specific random intercept and a time and subject-specific error term. The treatment effect of interest will be the interaction, representing the difference in mean change from pre-treatment to post-treatment between TranS-C and PE. The model will also provide estimates of the mean pre-to-post change in the PE condition (coefficient of Time) and in the TranS-C condition (coefficient of Time plus interaction coefficient), and the significance of these changes will also be reported regardless of the significance of the interaction because PE may be an active control and can be beneficial. Using Hochberg's procedure, the outcomes will be considered two subfamilies of analyses. The error rate in each subfamily will be controlled under 0.025 using the Hochberg's step-up procedure, so that the overall family-wise error rate will not exceed 0.05.

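### Age and sex enter the model as main effects only, so for youths with both assessments they cancel from the Time by Treatment effect

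*Combined protocol and SAP*

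**What the plan says.** Section 5 (Data Analysis) states: "All analyses will be adjusted for age and sex, which will be the stratification factors used during randomization". It then sets out the model. The fixed part is "The fixed component of the model will include stratification factors (age and sex), an indicator for time period", an indicator for arm, "and a Time by Treatment interaction term". For the rest, "The random part of the model will include a subject-specific random intercept and a time and subject-specific error term". The target is explicit: "The treatment effect of interest will be the interaction, representing the difference in mean change from pre-treatment to post-treatment between TranS-C and PE".

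No age by Time or sex by Time term appears. The section does not say whether age enters in years or as the two groups used for allocation, which section 2.1 describes as "stratified by sex and age (10-14, 15-18), in a 1:1 parallel group design".

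Three other features of section 5 bear on the point:

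- Incomplete pairs are expected: "We will recruit 20% more for potential attrition".
- They stay in the analysis: "multilevel modeling with maximum likelihood estimation with the assumption of missing at random will be used to examine continuous outcomes".
- The Time coefficient is given a meaning of its own (mean change under PE), as is Time plus the interaction (mean change under TranS-C). Both are to be reported whatever the interaction shows.

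**The concern.** A reader told that the analysis adjusts for the stratification factors will take the treatment contrast to be adjusted for them. In a two-occasion model whose target is a difference in change, main effects of fixed characteristics describe only a youth's overall level, and the change removes that level.

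If age or sex predicts how much a youth changes, that variation stays in the residual. The reported standard error then takes no credit for the balance that stratified allocation provides. The plan gives some reason to expect age to be related to outcome: section 1 describes eveningness as shifting with puberty, and section 2.2 sets later sleep-onset cut-offs for older youths. It gives no figure for an effect of age or sex on pre-to-post change.

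**Working it through.** **1. The plan's own figure.** With d = 0.48, power 80% and alpha 0.05 (two-sided, an assumption, since sidedness is not stated), n per arm = 2 × (1.960 + 0.842)² / 0.48² = 15.70 / 0.2304 = 68.1, rounded up to 69. This agrees with section 5. The calculation takes no credit for covariates, so nothing below changes it.

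**2. Algebra for complete pairs.** For youth i at time t (0 or 1), the planned model is

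y(i,t) = b0 + b1·age + b2·sex + b3·t + b4·trt + b5·t·trt + u(i) + e(i,t).

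Subtracting the pre value from the post value gives D(i) = b3 + b5·trt + e(i,1) − e(i,0). The terms b1·age, b2·sex and u(i) have gone. The estimate of b5 is the raw difference in mean D between arms, with or without age and sex, and its standard error depends only on the variance of D. This holds for age in years or in two groups.

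**3. Numerical check, complete pairs.** Data were simulated with 83 per arm (69 × 1.2 = 82.8) and fitted by maximum likelihood. In one dataset the interaction was 0.67959 (SE 0.1569) both without age and sex and with them as planned. The difference was zero in every complete-data run.

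**4. Precision forgone.** If the strata explain a share R² of the variance of change, the planned standard error is too large by 1/√(1 − R²) − 1, equivalent to 1/(1 − R²) − 1 of the sample. The documents give no R², so a range is assumed:

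| Assumed R² | SE too large by | Share of sample |
|---|---|---|
| 0% | 0% | 0% |
| 2% | 1.0% | 2% |
| 5% | 2.6% | 5% |
| 10% | 5.4% | 11% |

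Simulation agrees in size (1,000 runs per setting, assumed within-youth correlation 0.5). With an assumed age effect on change of 0.3 SD per 2.5 years, adding covariate by Time terms took the mean SE from 0.1613 to 0.1533, about 5% lower. With no age effect it went from 0.1545 to 0.1538.

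The spread of the estimates themselves fell less in the first case, from 0.1581 to 0.1557. Stratified allocation already balances these factors, so part of the gain is a reported SE closer to the true spread.

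**5. Incomplete pairs.** A youth with only one occasion has no difference to take, so the main effects enter the likelihood for b5.

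- With 17–20% dropout at random, over correlations 0.3 to 0.7, they moved the estimate by 0.008 to 0.027 SD on average and lowered the SE by 1% or less.
- With dropout strongly dependent on age and arm (assumed 5% v 35%, in opposite directions by arm) and a true effect of 0.48, the mean estimates were:

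| Age effect on change | Correlation | No covariates | As planned | With Time terms added |
|---|---|---|---|---|
| none | 0.3 | 0.391 | 0.484 | 0.484 |
| none | 0.5 | 0.425 | 0.491 | 0.490 |
| none | 0.7 | 0.436 | 0.475 | 0.475 |
| 0.3 SD per 2.5 years | 0.5 | 0.308 | 0.394 | 0.472 |

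In the last row the planned model falls short by (0.48 − 0.394)/0.48 = 18%. The dropout pattern is deliberately severe and is not drawn from the documents.

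**6. Effect of the remedy on the Time coefficient.** In one simulated dataset the planned Time coefficient was 0.116. With uncentred covariate by Time terms it became −0.043, the change in a reference cell rather than the PE mean. With centred covariates it was 0.126.

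**The case against.** The strongest reply has four parts.

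- The trial does not plan on complete data. It over-recruits for attrition and relies on likelihood estimation under missing at random, and there the main effects do work: in the first three rows of the dropout table they remove nearly all the bias. This stands. A reader might infer that the adjustment does nothing, or that the statement of adjustment is simply untrue. The documents do not support that, because the cancellation is exact only for complete pairs.
- Nothing here biases the treatment effect in complete data, and a standard error that is too large errs on the cautious side. This stands too. A reader might infer a biased result or an inadequate sample size, and neither follows.
- The size of the loss rests on an assumed link between age or sex and change. Treatment is six weekly sessions during the school year, timed to limit schedule variability. This is a fair limit, and the lower end of the range is almost no loss.
- Adding interactions carelessly would break the stated meaning of the Time coefficient, which the plan intends to report. This is correct, and the remedy has to provide for it.

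The reply does not remove the core point. For youths with both assessments, the contrast of interest is the same with the age and sex terms as without them.

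**Conclusion.** The point holds in a limited form. As specified, the age and sex adjustment leaves the interaction and its standard error unchanged for complete pairs. This follows from the model as written and needs no assumption about the data. Under attrition the main effects shift the estimate, usually slightly, and can reduce bias when dropout depends on age or sex.

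The possible loss is modest: a standard error about 1.0% to 5.4% too large if the strata explain an assumed 2% to 10% of the variance of change, and almost no loss if they explain none. There is also weaker protection if dropout depends on age and arm while change depends on age. The simulated figures rest on assumed correlations, age effects and dropout patterns. This is a nearly free improvement in precision and clarity, not a threat to validity.

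**What to change.** In section 5, keep the age and sex main effects and add age-group by Time and sex by Time to the fixed part, with age group defined by the two strata of section 2.1. State how age is coded.

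Centre both covariates at their sample means, or report the within-arm changes as marginal contrasts. The Time coefficient, and Time plus the interaction, will then still give the mean PE and TranS-C changes at average covariate values.

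The cost is a sentence or two of text and two extra parameters, with no new data or procedures and no change to the sample size. If age and sex turn out not to predict change, the effect on precision is negligible.

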### 2.2. Participants

Participants will be recruited through clinicians or advertisements. Individuals will be eligible if they (a) are between 10 and 18 years old, living with a parent or guardian, and attending a class/job by 9am at least 3 days per week; (b) are fluent in English; (c) are able and willing to give informed assent; and (d) report eveningness as demonstrated by scoring within the lowest quartile of the Children's Morningness-Eveningness Preferences Scale (CMEP; 27 or lower) and have a 7-day sleep diary showing a sleep onset time of 10:40pm or later for 10-13 year olds, 11pm or later for 14-16 year olds, and 11:20pm or later for 17-18 year olds at least 3 nights per week. In addition, this sleep pattern will have to have been present for the past 3 months. Finally, participants will have to fall into an 'at risk' range on measures of at least one of the five health domains reviewed above.

Exclusion criteria will be (a) an active, progressive physical illness or neurological degenerative disease directly related to the onset and course of the sleep disturbance; (b) evidence of obstructive sleep apnea, restless legs syndrome, or periodic limb movement disorder; (c) significantly impairing pervasive developmental disorder; (d) bipolar disorder, schizophrenia, or another current Axis I disorder if there is a risk of harm if treatment is delayed. Participants will cease taking medications that alter sleep (e.g., hypnotics) 4 weeks prior to the assessment (2 weeks for melatonin) or will be excluded. Finally, history of substance dependence in the past six months or current suicide risk sufficient to preclude treatment on an outpatient basis will be exclusionary.

In other words, receipt of another sleep treatment will be the only type of treatment excluded. We want to be sure that any improvements in sleep could be attributed to TranS-C or PE, not the other sleep treatment. Other medications will be allowed. A medication-free group would be unrepresentative. We will also include youth with Axis I psychiatric comorbidity (except for bipolar disorder and schizophrenia), even if they are receiving treatment for that comorbidity.

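### Siblings are randomised together but analysed as independent, so the treatment effect's standard error is too small if their changes are positively correlated (minor)

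*Combined protocol and SAP*

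**What the plan says.** Section 2.1 describes individual allocation: "youth will be randomly assigned, stratified by sex and age (10-14, 15-18), in a 1:1 parallel group design". It then makes an exception: "Sibling pairs will be randomized to the same condition".

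Section 5 states the model in full. Its fixed part is introduced as "The fixed component of the model will include stratification factors (age and sex), an indicator for time period", followed by treatment condition and the interaction of time with treatment. Its random part is described so: "The random part of the model will include a subject-specific random intercept and a time and subject-specific error term". The estimate that matters is also named: "The treatment effect of interest will be the interaction, representing the difference in mean change from pre-treatment to post-treatment between TranS-C and PE".

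On error control, section 5 states: "The error rate in each subfamily will be controlled under 0.025", by Hochberg's procedure, so that the overall rate stays within 0.05. On size it states: "Sixty nine participants are needed for each condition. We will recruit 20% more for potential attrition".

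The document contains no family random effect, no family-clustered standard error, no sensitivity analysis with one sibling per family, and no allowance for siblings in the sample size. It does not give an expected number of sibling pairs or a within-family correlation.

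**The concern.** The design foresees siblings and binds them to one arm, but the analysis ignores that binding. Two siblings in one arm contribute to the same arm mean. If one improving makes it more likely that the other improves, the pair carries less information than two unrelated participants. The model counts them as two independent participants.

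The relevant correlation is that of the pre-to-post **change**, because the treatment effect is a difference in mean change. A family level that is the same at both visits cancels from the change and does no harm. For the same reason, adding only a family random intercept would not correct the interaction.

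A positive correlation of change is plausible. Participants must live with a parent or guardian (section 2.2), so siblings will usually share a household, and one parent may rate both children on the CBCL (section 3.4.3). If the correlation is positive, the interaction's standard error is understated, and the stated limits of 0.025 per subfamily and 0.05 overall are not assured.

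**Working it through.** **1. The plan's own figure.** Inputs from section 5: d = 0.48, significance 0.05 (taken as two-sided) and power 80%. Then n per arm = 2 × ((1.960 + 0.842)/0.48)² = 68.13, rounded up to 69. This reproduces the stated 69. A noncentral t calculation gives 70, with power 79.94% at 69. The calculation assumes independent participants. Adding 20% gives 69 × 1.2 = 82.8, about 83 per arm.

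**2. Design effect.** Let an arm have n participants, of whom 2m are in m sibling pairs. Let σ² be the variance of the change and r its within-pair correlation. Then

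Var(mean change) = (nσ² + 2m·r·σ²)/n² = (σ²/n)(1 + f·r), with f = 2m/n.

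So DE = 1 + f·r, and the true standard error is √DE times the model's. For a test with two-sided critical value z, the actual error is 2 × (1 − Φ(z/√DE)), with z = 2.241 for 0.025 and 1.960 for 0.05.

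**3. Assumed inputs.** Neither f nor r is in the documents. Recruitment is not family-based ("Participants will be recruited through clinicians or advertisements", section 2.2), so f = 5–10% is taken as the likely range. That is 83 × 0.05/2 ≈ 2 to 83 × 0.10/2 ≈ 4 pairs per arm. The bounding case of f = 30% is about 12 pairs per arm.

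| f | r | DE | SE increase | Error at nominal 0.025 | Error at nominal 0.05 |
|---|---|---|---|---|---|
| any | 0 | 1.000 | 0% | 0.0250 | 0.0500 |
| 5% | 0.3 | 1.015 | 0.75% | 0.0261 | 0.0517 |
| 10% | 0.3 | 1.030 | 1.49% | 0.0272 | 0.0535 |
| 30% | 0.5 | 1.150 | 7.24% | 0.0366 | 0.0676 |

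**4. Check of the formula.** In 20,000 simulated trials with 69 per arm, 7 pairs per arm (f ≈ 20%) and r = 0.5, the error at nominal 0.05 was 0.062. The formula gives 0.0617. With a family level shared at both visits but r = 0 for change, the error was 0.048, so there was no inflation.

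**5. Error per subfamily under Hochberg.** Section 5 does not list the members of the subfamilies. Three or five outcomes with correlation 0.3–0.5 are therefore assumed (2,000,000 draws of test statistics scaled by √DE, limit 0.025):

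- no pairs: 0.022–0.024
- f = 5%, r = 0.3: 0.023–0.026
- f = 10%, r = 0.3: 0.025–0.027
- f = 30%, r = 0.5: 0.038–0.042

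Hochberg's procedure is slightly conservative for correlated outcomes. That margin roughly absorbs the sibling effect when pairs are few.

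**6. Check of the fix.** In 100,000 simulated trials of complete change scores, 83 per arm, nominal 0.025, the error rates were:

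| Pairs per arm | r | Unadjusted | Clustered on family |
|---|---|---|---|
| 12 | 0.5 | 0.037 | 0.027 |
| 4 | 0.3 | 0.028 | 0.026 |
| 12 | 0 | 0.026 | 0.026 |

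**The case against.** The strongest reply is that in the likely case almost nothing changes. Both siblings would have to meet every entry criterion in section 2.2: the CMEP cut-off, late sleep onset on at least 3 nights per week, a 3-month history and an at-risk domain. Few pairs should result. At f = 5–10% and r = 0.3 the subfamily error exceeds 0.025 by at most about 0.002. This stands, and it is why the point is minor.

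The correlation is also unsupported by any figure. Being in the same arm is no reason for it, since the model already contains the arm effect. Sessions are individual (section 2.3) and TranS-C is tailored to each patient (section 2.3.1). This stands as far as size is concerned. It does not exclude a correlation, because siblings usually share a home and parents.

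Finally, clustering does not bring the error exactly to 0.025. The simulations show 0.026 with r = 0, and a separate check with maximum-likelihood variance and a normal reference gave 0.027 with no pairs at all. That remainder is a large-sample approximation unrelated to siblings, and at f = 5–10% it is similar in size to the sibling effect. Clustering removes the sibling part only. The fix was also tested on complete change scores, not on the full mixed model with missing data.

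**Conclusion.** The concern holds, in conditional form, as a minor one. The text is clear that siblings are allocated together and that the model treats them as independent. Whether this matters depends on two quantities that the documents do not give.

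With few pairs and a moderate correlation, the standard error is understated by about 1% and the 0.025 limit is roughly held. The limit is clearly exceeded only in the bounding case of about 12 pairs per arm with r = 0.5, which nothing in the documents suggests is likely. With no correlation of change there is no bias.

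The sample size of 69 per arm is correct on its own inputs. Allowing for siblings would raise it to 70 or 71 in the likely range (68.13 × 1.015 = 69.2; 68.13 × 1.03 = 70.2).

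The case for acting is that section 5 gives its error guarantee without condition, no section caps the number of sibling pairs, and the handling of siblings is best settled before results are seen.

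**What to change.** Add to section 5: *Standard errors are clustered on family (Stata vce(cluster family ID)), with participants without an enrolled sibling forming their own cluster. The number of sibling pairs per arm will be reported.*

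This follows the unit of randomisation, allows for correlated changes and works with the planned maximum likelihood estimation. A family random effect on time as well as on the intercept would be an alternative; a family random intercept alone would not do.

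The cost is two sentences and a family identifier in the dataset. Confidence intervals may be slightly wider. Design and recruitment are unchanged.

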#### **3.3. Circadian Outcomes**

##### **3.3.1 Children's Morningness-Eveningness Preferences Scale (CMEP)**

CMEP will be a primary outcome. Scores range from 10 (Extreme evening preference) to 43 (Extreme morning preference).

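### CMEP: if the analysed baseline carries the entry cut-off, the equal-variance model makes the interaction's standard error slightly too small when post-treatment scores are missing, and can bias it

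*Combined protocol and SAP*

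**What the plan says.** Section 5 (Data Analysis) analyses continuous outcomes at two time points, with fixed effects for age, sex, time, treatment and their time-by-treatment interaction. On the covariance it says: "The random part of the model will include a subject-specific random intercept and a time and subject-specific error term". On estimation: "multilevel modeling with maximum likelihood estimation with the assumption of missing at random will be used". No residual variance by time, robust standard error or small-sample degrees of freedom is mentioned. Each of two subfamilies of outcomes is to be held at 0.025.

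Section 2.2 requires "scoring within the lowest quartile of the Children's Morningness-Eveningness Preferences Scale", given as 27 or lower. Section 3.3.1 says "CMEP will be a primary outcome". Section 5 expects losses: "We will recruit 20% more for potential attrition".

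Section 4 has questionnaires completed at an in-person assessment, after which criteria are checked again. The diary is collected afresh after randomization. No passage says which CMEP administration supplies the pre-treatment value.

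**The concern.** A random intercept with a single residual variance implies the same variance at both times. If the analysed CMEP baseline has been cut at the lowest quartile, that cannot be right: the cut shrinks the pre-treatment spread, and post-treatment scores are free to spread out again.

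When a post-treatment score is missing, the model uses the participant's baseline, through its implied slope of post on pre, to estimate the arm's post-treatment mean. A wrong common variance gives a wrong slope and a wrong residual variance. The reported standard error is then off. If completers differ from all randomized participants in baseline CMEP by different amounts in the two arms, the interaction is also biased, even when missing at random holds exactly. At stake are the stated 0.025 level for a primary outcome and the protection that the missing-at-random analysis is meant to give.

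**Working it through.** **The plan's sample size.** Section 5 uses d = 0.48 ("0.48) across estimations of the effect of treatment on sleep duration"), "assuming significance of 0.05 and power of at least 80"%, and concludes "Sixty nine participants are needed for each condition". Two-sided, n = 2(1.960 + 0.842)²/0.48² = 68.1, so 69; the figure is reproduced. Adding 20% gives 69 × 1.2 = 82.8, so 83 per arm. If 69 complete, 14/83 = 16.9% are missing after treatment.

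**Assumptions not in the documents.** CMEP is normal in the source population with SD 1. The analysed baseline is the screening score, cut at the lower quartile. The pre-post correlation r in the uncut population is 0.5 to 0.85. There is no true effect, and covariates are ignored.

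**Variances, shown for r = 0.7.**
- With c = -0.6745 and λ = φ(c)/0.25 = 1.2711, the baseline variance is V1 = 1 - cλ - λ² = 1 + 0.8573 - 1.6157 = 0.2416 (SD 0.49).
- Covariance C = rV1 = 0.1691. Post-treatment variance V2 = r²V1 + 1 - r² = 0.6284.
- Post/pre SD ratio = √(0.6284/0.2416) = 1.61. It is 1.83 at r = 0.5 and 1.37 at r = 0.85.

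**Complete pairs.** The fitted common variance is s = (V1 + V2)/2 = 0.4350 and the fitted correlation is ρ = 2C/(V1 + V2) = 0.389. The model's variance of change is 2s(1 - ρ) = V1 + V2 - 2C = 0.532, which is the true value. The choice of covariance does no harm.

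**69 of 83 observed, loss unrelated to anything.** The large-sample fit gives s = 0.4150 and ρ = 0.376. Under equal variances ρ is also the post-on-pre slope; the true slope is 0.70.
- The arm's estimated change is the completers' mean of (post - ρ·pre) minus (1 - ρ) times the mean baseline of all.
- Model variance = s[(1 - ρ²)/69 + (1 - ρ)²/83] = 0.007113.
- True variance = (V2 + ρ²V1 - 2ρC)/69 + [(1 - ρ)²V1 - 2(1 - ρ)(C - ρV1)]/83 = 0.007715.
- SE ratio = √(0.007113/0.007715) = 0.960. Type I error at nominal 0.025 = 2Φ(-2.2414 × 0.960) = 3.1%.

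| r | True slope | Fitted slope | SE ratio | Type I error at 2.5% |
|---|---|---|---|---|
| 0.50 | 0.50 | 0.22 | 0.951 | 3.3% |
| 0.70 | 0.70 | 0.38 | 0.960 | 3.1% |
| 0.85 | 0.85 | 0.58 | 0.973 | 2.9% |

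Maximum likelihood with normal-theory tests adds a separate error: about 2.8% at nominal 2.5% with 138 complete participants, or 0.3 points.

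**Bias.** Each arm's post-treatment mean is off by (fitted slope - true slope) × (baseline mean of all - baseline mean of completers). In the truncated baseline, the halves below and above the median differ in mean by 0.751. At r = 0.7 the slope error is 0.376 - 0.700 = -0.324.
- *Unequal rates (10% v 24%), unrelated to baseline:* the baseline gap is zero in both arms, so the bias is zero.
- *Both arms lose more low scorers, at unequal rates* (15% low and 5% high v 36% and 12%): low scorers are 0.85/1.80 = 0.472 and 0.64/1.52 = 0.421 of completers. The gaps are -(0.5 - 0.472) × 0.751 = -0.021 and -(0.5 - 0.421) × 0.751 = -0.059. Bias = 0.324 × 0.038 = 0.012. The planned effect is 0.48 × √0.532 = 0.350, so this is about 3.5% of it; about 2-4% across r.
- *Opposite selection* (25.5% low and 8.5% high in one arm, reversed in the other): low scorers are 0.745/1.66 = 0.449 of completers in one arm, so the gap is (0.5 - 0.449) × 0.751 = 0.0385 in size, with opposite signs. Bias = 0.324 × 0.077 = 0.025, about 7%; 5-8% across r.
- *Stronger drop-out dependence in one arm* gave 3.5-4.7% of the SD of change in simulation; divided by 0.48, that is about 7-10%.

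**Other readings of Time=0.** If CMEP is repeated in person and again held to 27 or lower (retest 0.8-0.9), the SE is 2-5% too small. If it is repeated with no second cut-off, the SE ratio is 0.98-1.00.

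**Unstructured covariance.** In simulation this brought the bias to at most 0.003 population SD. With t-based tests, type I error was 2.2-2.6% at nominal 2.5%.

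**The case against.** **The premise may fail.** The plan never says that the screening CMEP is Time=0, and a re-measure without a second cut-off nearly removes the effect. This stands. Against it, Section 4 describes one pre-treatment questionnaire occasion with a further check of criteria, re-collects the diary but does not mention CMEP there, and Section 2.1 randomizes only once eligibility assessment is finished. A baseline subject to the cut-off is therefore plausible, but not established.

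**The wording may allow unequal variances.** An error term described as specific to time and subject most naturally just indexes one residual, but it does not exclude a variance for each time. One sentence in the plan would settle it.

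**A reader might extend the point to all primary outcomes.** The documents do not support that. The sleep-onset rule is applied to a screening diary, while the analysed diary is collected after randomization. The outcomes are total sleep time and time of getting into bed, not sleep onset, and total sleep time has no entry cut-off. The self-report composite is selected only through risk in any one of five domains.

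**A reader might infer that differential drop-out by itself biases the result.** It does not. Drop-out must also depend on baseline CMEP, and differently by arm. No passage predicts this, although only TranS-C participants are encouraged to keep a diary during treatment (Section 2.3).

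**A reader might infer that the family-wise claim collapses.** With 3 to 8 independent outcomes in the subfamily (an assumed number) and only CMEP affected, that subfamily's error is about 2.6-2.9%. Adding 2.5% for the other gives roughly 5.1-5.4% overall. The bound is not strictly secured, but the excess is small.

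**Conclusion.** The point holds for CMEP, conditionally, and is of minor to moderate weight. If Time=0 is a score subject to the entry cut-off and post-treatment values are missing, the stated model is misspecified in the anti-conservative direction. For a screening score used as Time=0 with 17% random loss, the standard error is about 3-5% too small and single-test error is 2.9-3.3% instead of 2.5%, before the separate 0.3 points from ML with normal-theory tests. Bias arises only under baseline-dependent drop-out that differs by arm, at roughly 2-10% of the planned effect for the patterns tried. With complete pairs there is no error. The point is weak or absent for total sleep time, bedtime and the self-report composite.

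The direction follows from the model. The sizes rest on assumed normality, correlations and drop-out, and they treat the whole recruitment margin as realised loss; the documents give no SDs, correlations or drop-out pattern.

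**What to change.** Keep the fixed effects as written. Replace the random intercept and single residual with an unstructured 2x2 (pre, post) residual covariance, or state that residual variance may differ by time. Fit by restricted maximum likelihood with Kenward-Roger or Satterthwaite degrees of freedom. State which CMEP administration is Time=0 and whether it was subject to the 27-or-lower rule.

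The cost is a few words in Section 5, one extra variance parameter and slightly less favourable p-values. The planned sample size and the treatment effect being estimated do not change, and little is lost if the two variances turn out equal.
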